5.4 Exit

Three months after completing Secure or 3 months after the last engagement with the Pivot app (whichever comes first), the participant is asked to complete the final follow-up questionnaire and return the CO Breath Sensor in the provided pre-paid package. Upon completion of the final survey and return of the CO Breath Sensor, the study will be considered complete.

6 Study Results

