
feedback on the experience is sought upon completion of the Secure phase of the Pivot App, or upon the end of the participant's engagement with the app, whichever occurs first. Upon return of the study device and completion of the questionnaire conducted 3 months after completing the primary phase of the

study, the study is considered complete.

Endpoint and analysis

We will compare the following variables at entry, after completion of each Pivot App phase, and/or at exit.

Engagement:

- Weeks of active engagement
- Phase completion
- Number of app opens

Smoking Behavior:

- Number of cigarettes smoked per day
- Quit attempts
- Quit rates: 7-day, 30-day point prevalence
- Sustained quit (continuous days quit)
- Smoking reduction (in participants who do not quit)

Responses to questionnaires:

- Measurements assessing attitude toward smoking
 - Readiness to quit
 - o Goals related to smoking behavior
 - Confidence to quit
 - o Difficulty maintaining quit
- Net Promoter Score (NPS)
- NPS, Coaching
- Nicotine Dependence
- Quality of Life

Schedule of Study Activities

	Screening	Day 0	Day 1	Pivot App - Explore (9 days)	Pivot App - Build (1 - 28 days)	Pivot App - Mobilize (7 days)	Pivot App - Quit (7 days)	Pivot App - Secure (11 weeks)	Exit - 3 mos after Secure or 3 mos after the end of participant's engagement with the app
Eligibility Confirmed	Х								
Informed Consent		Х							
Baseline Questions (demographics, thoughts about smoking)		Х	Х	х					
Receive COBSS*			Х						
Cigarette Logging**				Х	Х	Х	Х	Х	
Breath Sampling***				Х	Х	X	Х	Х	
Coach-Initiated Interactions				Х	Х	X	Х	Х	
Questionnaire			Х	Х	X	х	Х	Х	Х
Questionnaire (thoughts about smoking and the experience of using the device)								Х	
Exit questionnaire									Х
Return Breath Sensor									X
Study Completion									Х

^{*} COBSS received by participant only after confirmation of eligibility and provision of informed consent

^{**} Cigarette logging should stop at the beginning of the Quit phase of the Pivot App (assuming participant quits smoking), however, participants are asked to log all cigarettes, including those that occur during a lapse or relapse

^{***} Suggested breath sampling schedule varies from one phase to the next

Table of Contents

1		In	roduction 9		
	1.1		Background		9
	1.2		Study Rationale		10
	1.3		Potential Risks a	and Benefits	10
	1	.3.	1 Known Pot	tential Risks	10
	1	.3.	2 Known Pot	tential Benefits	10
	1	.3.	Risk Benef	fit Assessment	10
2		St	udy Objective		11

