4.2 Study Endpoint

Primary endpoint:

- Phase completion of those who started a phase, the proportion who completed that phase, assessed for each phase of the Pivot program.
 - Phase completion is defined as completing the last in-app activity from that phase
 - Exception: completion of Secure is defined as being in Secure for 11 weeks, and having engaged with the program at least once within Secure (app open, daily check-in, responds to coach, logs cig), and providing smoking status (cigarettes per day and 7-day point prevalence) in the end-of-Secure questionnaire

Additional endpoints include:

Engagement:

- Weeks of active engagement
- Number of app opens
- Phase completion proportion of intention to treat (ITT) cohort that completes each phase
 - ITT cohort comprises participants who signed informed consent and completed onboarding in the Pivot app (i.e. downloaded the BSA and Pivot apps, completed device set-up, and completed the three guided breath tests, or GBTs)
- Program completion proportion of intention to treat (ITT) cohort who have been in Secure for 11 weeks and have engaged with the program at least once (open app, or complete a daily check-in, or respond to coach, or log a cigarette), and, provides smoking status (cigarettes per day and 7-day point prevalence) in end-of-Secure Survey

Smoking Behavior:

- Number of cigarettes smoked per day
- Quit attempts (participant did not smoke for at least 24 hours)
- Quit rates: 7-day, 30-day point prevalence

CONFIDENTIAL

- Assessed in the ITT cohort
- Assessed in the Per Protocol cohort (individuals who complete the end-of-phase survey in the phase during which the question is being asked or, complete the exit survey at the end of their engagement with the app, whichever occurs first)
- Sustained quit (continuous days quit)
 - Assessed in the ITT cohort
 - Assessed in the Per Protocol cohort
- Smoking reduction (in participants who do not quit smoking) proportion who achieved 50% cigarettes per day (CPD) reduction or more at study exit

Responses to questionnaires:

- Measurements assessing attitude toward smoking
 - o Readiness to quit
 - Goals related to smoking behavior
 - Confidence to quit
 - o Difficulty maintaining quit
- Net Promoter Score (NPS)
- NPS, for coaching
- Nicotine Dependence
- · Quality of Life

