5.3 Pivot Journey

After set-up and onboarding, participants start the Pivot program. The Pivot program consists of four primary components:

- Periodic breath sampling using the CO Breath Sensor
- Cigarette logging
- Daily activities and challenges
- Coaching using in-app chat

During the study, participants submit periodic breath samples (suggested frequency is phase-dependent) while awake. Participants are instructed to log each cigarette they smoke using the Pivot app.

Participants are also asked to complete the activities presented in the Pivot app. Pivot app activities are educational in nature and intended to facilitate exploration and understanding of one's smoking behavior and attitudes. In addition, Build (the second phase of the program) includes challenges associated with activities; these challenges enable participants to develop skills to assist with quitting

In addition, participants will engage with a coach. The coach will initiate interactions with the participant by in-app chat throughout each phase of the study. The coach's primary role is to partner with the participant to explore how smoking impacts their time and financial resources, what purpose smoking serves in their life, their reasons for why they might want to quit, their interest and readiness in quitting, and provide support and encouragement during the quit process.

The Pivot program consists of 5 phases that are intended to be completed sequentially, with continuous engagement (i.e. no breaks in between). Acknowledging that challenging life events and circumstances occur, participants will be permitted to resume the Pivot program where they left off after up to two weeks of non-engagement/absence.

		-		
Δ	summary of each	i Pivot nhaca ic i	nravidad halawi	i
$\overline{}$	Summary of Cach	i i ivot pilase is i	provided below	
	,			

Explore			
Duration, pace, key components	 9 days, time based, one activity unlocks each 24 hours 		
Intent	 "Open the Door" "Turn on the light bulb" Raise awareness and build motivation 		
Activity/content	One activity is unlocked per 24h		
Cigarette logging	All cigs		
Suggested breath CO sampling protocol	 Hourly samples (10) a day for 9 days 		
Coaching frequency	4 coach-initiated touch-points in 9 days		

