Study management	 If participant does not use the app at least once during the 2 days after onboarding (no cig logging, or CO sampling, or start/complete activity, or respond to coach outreach), study staff will call participant on days 3, 4 and 6 		

Build		
Duration, pace, key components	 1 day to 4 weeks based on recommended daily pace. Can be longer if content is not consumed daily. Daily activity+challenge available 	
Intent	 For those ready to quit, make a quit plan For those not yet ready to quit, raise readiness and confidence, then make a quit plan 	
Activity/Content	 28 activities and 28 associated challenges in 4 modules (7 activities and 7 challenges per): Prep to Quit (PTQ) Smoking & Health Motivation Matters Potential Pitfalls User starts on a specific module based on their responses to final Activity (9) of Explore. Users whose responses indicate they are ready to quit (score of 8 or higher on each of 3 questions about readiness, confidence and perceived difficulty of quitting), go straight to PTQ. Otherwise another module is prioritized. User must choose a quit date to unlock PTQ User can spend 1 day to 4 weeks in Build, or longer if they do the activities slower than daily 	
Cigarette logging	All cigs	
Suggested breath CO sampling protocol	Hourly samples throughout Build	
Coaching frequency	 3 to 4 touch-points per week If a user has not completed activities and/or hasn't had a coaching interaction within 3 days, the coach will reach out to the user to check in. 	
Study management	If participant does not use the app at least once in 7 days (no cig logging, or CO sampling, or start/complete activity, or start/complete challenge, or complete daily check-in, or respond to coach outreach), study staff will email on day 9, text on day 10, call on day 11, and call on day 13	

Mobilize				
Duration, pace, key components	7 days based on recommended daily pace			
Intent	Prepare for Quit Day			
Activity/content	 7 activities, daily pace recommended No time lock, but must finish all activities to move on User can finish faster or slower. Quit date must be set within 14 days, but user can push out quit date during Mobilize, and thus extend this phase of the program User prompted to change quit date if not all activities are completed User prompted to set earlier quit date if they finish all activities. 			
Cigarette logging	All cigs			

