Cigarette logging	Daily check-in asks if user smoked previous day, if so, then directs them to log cig.
Suggested breath CO sampling protocol	No explicit sensor use schedule, but sensor is incorporated as follows: • Encourage people who find the 3 times a day useful to keep doing that. • Allow users to set their own milestones, some can be sensor related. Pivot app also gives trophies for breath samples associated with abstinence to augment this. "Take a breath samples to celebrate your smoke-free success."
Coaching frequency	 3-4 coach-initiated interactions per week for the first 3 weeks For users who achieve 30day PP at 3 weeks or 7 weeks in Secure, coaching frequency drops to once weekly, until/unless user indicates lapse or relapse.
Study management	 For the first 3 weeks: If participant does not use the app at least once in 7 days (no cig logging, or CO sampling, or start/complete activity, or start/complete challenge, or complete daily check-in, or respond to coach outreach), study staff will email on day 9, text on day 10, call on day 12, and call on day 14 For the remaining 7 weeks: If participant does not use the app at least once in 14 days (no cig logging, or CO sampling, or start/complete activity, or start/complete challenge, or complete daily check-in, or respond to coach outreach), study staff will email on day 16, text on day 17, call on day 19, and call on day 21

The following table details the different questions being asked of participants at specific time points over the course of the study.

		1	1	1	T	I	I	1	1	T
	Baseline	Explore	Build	Mobilize	Quit (1wk)	Secure - 1wk (2wk post Quit)	Secure - 3wk (1mo post Quit)	Secure - 7wk (2mo post Quit)	Secure - End (3mo post Quit)	Follow -up (6mo)
Cigarettes per day	х	Х	Х	х	х	Х	Х	Х	х	х
Tobacco Forms Used	Х		Х		Х		х	Х	Х	Х
Readiness to Quit (1-10)	х	Х	Х	Х						
Success, if were to quit (1-10)	х	х	Х	Х						
Difficulty staying quit, (1-10)	Х	Х	Х	Х						
Quitting Goal	х	Х	Х	х						
Nicotine Dependence		Х		Х						
7day Point Prevalence					х	х	х	Х	Х	х
30day Point Prevalence							х	Х	Х	х
Date of Last Cig					Х	Х	Х	Х	х	Х
Longest Smoke- free Interval					Х	X	X	Х	Х	Х
Quit Attempts					Х	Х	Х	Х	х	Х
NPS		Х	Х	Х	Х				х	
Coach NPS		X	Х	Х	Х				Х	
Quality of Life	Х								Х	Х
Cessation Medications	х			Х	х	×	×	Х		Х

Participants will receive an email, text or phone call from study staff to inform them they have a questionnaire to complete (

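### The final questionnaire labelled 6 months falls due about 3.0 to 7.2 months after entry at nominal phase lengths, depending on how long the participant used the app

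*Combined protocol and SAP*

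**What the plan says.** The plan gives several anchors for one questionnaire.

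- Section 5.4: "Three months after completing Secure or 3 months after the last engagement with the Pivot app (whichever comes first", that is, the earlier of two dates.
- Schedule of Study Activities: "Exit - 3 mos after Secure or 3 mos after the end of participant's engagement with the app", both anchors with no rule for choosing between them.
- Section 4.10: the last time point is 3 months after Secure ends, with no second trigger.
- Section 1.2: a 3-month program, then 3 months of follow-up once the program is complete.
- Protocol Summary and section 4.1: 3 months after the primary phase, which can be read either way for someone who stops early.
- Section 5.3 questionnaire table: the last column is labelled as 6 months. The column before it reads "Secure - End (3mo post Quit", so the neighbouring labels count from the quit date. The protocol title also promises 6 months.

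Section 4.2 defines completing Secure as "being in Secure for 11 weeks, and having engaged with the program at least once within Secure", plus giving smoking status in the end-of-Secure questionnaire. It lists what counts as engagement there, and an app open is on the list. The staff-outreach lists in section 5.3 differ: inactivity in Secure means "no cig logging, or CO sampling, or start/complete activity, or start/complete challenge, or complete daily check-in, or respond to coach outreach". They name neither an app open nor a questionnaire.

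Section 4.2 sets the 50% reduction endpoint at study exit. Section 6.2 analyses change from baseline to exit as one time point, with no window and no split by trigger.

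**The concern.** Under section 5.4 the date of the final measurement is set by how long the person kept using the app. Weeks of active engagement is itself an endpoint in section 4.2, so follow-up time is tied to an outcome. People who stop early are asked about their smoking sooner after entry than people who stay.

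The plan fixes this time point expressly only for the 50% reduction endpoint. By inference from section 6.2 and the questionnaire table, exit quit rates (7-day and 30-day), sustained quit, cigarettes per day and quality of life share it. If these are summarised together under a 6-month label, the label is wrong for part of the cohort. Section 4.10 intends historical comparisons, and quit rates measured at different times are not interchangeable in such a comparison.

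**Working it through.** **Inputs.** Schedule of Study Activities: Explore 9 days, Build 1 to 28, Mobilize 7, Quit 7, Secure 11 weeks = 77 days. Protocol Summary: primary phase 14.5 to 18.5 weeks. Conversions used here: 3 months = 91 days, 1 month = 30.44 days.

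**Reproducing the plan's figure.** 9 + (1 to 28) + 7 + 7 + 77 = 101 to 128 days = 14.4 to 18.3 weeks, against 14.5 to 18.5 stated. This agrees when Secure starts after the Quit week. The section 5.3 summary of Secure instead counts its 11 weeks from the quit date (day 9 + (1 to 28) + 7 = 17 to 44). That gives 94 to 121 days, or 13.4 to 17.3 weeks, which does not agree.

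**Due date.** Due day = min(Secure completion, last engagement) + 91. Days since quit date = due day minus the quit date (day 17 to 44).

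| Last app use | Day of last use | Due day | Months after entry | Since quit date |
|---|---|---|---|---|
| Onboarding (day 1) | 1 | 92 | 3.0 | no quit date |
| End of Explore | 9 | 100 | 3.3 | no quit date |
| End of Build | 10–37 | 101–128 | 3.3–4.2 | quit date not reached |
| End of Quit | 24–51 | 115–142 | 3.8–4.7 | 98 d (3.2 mo) |
| Secure week 3 | 45–72 | 136–163 | 4.5–5.4 | 119 d (3.9 mo) |
| Secure week 7 | 73–100 | 164–191 | 5.4–6.3 | 147 d (4.8 mo) |
| End of Secure | 101–128 | 192–219 | 6.3–7.2 | 175 d (5.7 mo) |

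If Secure's 11 weeks run from the quit date, the last row becomes day 185–212 (6.1–7.0 months) after entry and 77 + 91 = 168 days (5.5 months) after the quit date.

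**Neither end of the last row is a limit.** Section 5.3 says of Mobilize: "User can finish faster or slower". A 1-day Mobilize gives 95 + 91 = day 186 (6.1 months). A 14-day Mobilize gives 128 + 7 + 91 = day 226 (7.4 months). Participants are also "permitted to resume the Pivot program where they left off after up to two weeks of non-engagement/absence". One 14-day absence that delays the journey gives 128 + 14 + 91 = day 233 (7.7 months), and both together give day 240 (7.9 months). Build has no cap.

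**Secure completers.** One engagement within Secure suffices for completion. Suppose it falls on Secure day 1 (day 25 to 52), and answering the end-of-Secure questionnaire does not count as engagement. The final questionnaire is then due on day 116 to 143. The end-of-Secure questionnaire falls on day 101 to 128, so the gap is 116 − 101 = 143 − 128 = 15 days. It is 116 − 94 = 22 days if Secure runs from the quit date, and 91 days for someone engaged to the end.

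**The case against.** The strongest defence is that a constant interval off program is a legitimate design. Section 1.2 states a 3 + 3 month intent, so 6 months can be read as a nominal label, and the Protocol Summary discloses that the primary phase varies with exit and re-entry. The trial has one arm, so no between-arm contrast is distorted. Smoking outcomes are also collected up to the end of Secure. All of this stands, and the fix below keeps the 3 months off program. It does not rescue the label: a person who stops at onboarding has about 0 + 3 months, not 3 + 3.

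A reader might infer three stronger things that the documents do not support.

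- *That the label fits no early leaver on any clock.* It does fit some. Someone who last used the app at Secure week 7 is due 5.4 to 6.3 months after entry, nearer to 6 than many full completers.
- *That the 15-day gap will occur.* Section 4.2 counts an app open as engagement, and section 4.1 says some questionnaires are answered in-app. If the end-of-Secure one is, last engagement falls at the end of Secure and the gap is about 91 days. The 15-day case also needs about 101 − 25 = 76 days of non-use, against the two-week absence after which section 5.3 permits resumption. It is a gap in the definition, not a demonstrated effect.
- *That the plan states it will pool the two triggers, or that the exit rates are biased in a known direction.* The plan names one exit time point and no way to separate the triggers. Pooling is inferred, and the direction of bias cannot be derived.

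**Conclusion.** The point holds and should be fixed before exit results are reported. Followed as written, section 5.4 spreads the final questionnaire over about 3.0 to 7.2 months after entry, and further if phases run long. A combined exit figure is therefore not a 6-month outcome and should not be compared with historical 6-month rates as if it were. On the quit-date clock the label suits people engaged to the end of Secure (5.7 months, or 5.5 if Secure runs from the quit date). It does not suit people who stop well before that, and those who never reach Quit have no such clock.

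This rests on nominal phase lengths, 3 months taken as 91 days, and section 5.4 being the operative rule. The primary endpoint, phase completion, does not use this questionnaire. Section 4.10 expects 100 or more of 260 at the last time point but does not say how many would answer on each trigger, so the share affected is unknown.

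**What to change.** 1. Reconcile the Protocol Summary, the Schedule of Study Activities and sections 1.2, 4.1, 4.10, 5.3 and 5.4, so that exit and the 6-month label each have one stated anchor and clock. Also reconcile the start of Secure: the schedule places its 11 weeks after Quit, while the section 5.3 summary counts them from the quit date. The outreach rule there covers a first 3 weeks and then "For the remaining 7 weeks", which is 10 weeks and fits the quit-date count.
2. Define last engagement. State whether the section 4.2 list or the section 5.3 lists apply, whether answering a questionnaire counts, and how a return after a permitted absence is handled.
3. Label the combined result as about 3 months after the end of program use. Report it on the full ITT denominator, which section 4.2 already requires for quit rates and sustained quit. Give the distribution of time since entry, and since the quit date where one exists. Show results separately by trigger (Secure completion versus earlier last engagement), as description only, because the trigger depends on app use.
4. Do not base a 6-month result only on people who happen to be measured in a window around 6 months. That selects on duration of app use; all ITT participants must stay in the denominator.

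The cost is some redrafting, a little more analysis and a less simple headline. No extra participant contact is needed, assuming that dates of entry, app use and questionnaires can be taken from the electronic records described in sections 3.1.2 and 6.1.

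A common send date for all ITT participants is a trade-off left to the sponsor. At 26 weeks (182 days, illustration only), someone who stopped on day 1 would be 182 − 1 = 181 days off program and a full completer 182 − 128 = 54 to 182 − 101 = 81 days, so one unevenness replaces another.

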6.1 Data Collection and Confidentiality

Data collection will be electronically administered through participant input in the Pivot online registration form, BSA and Pivot apps, and online questionnaires. As it is entered by the participant, the study data directly populates a secure database. This database is user ID and password protected and will be accessible only by necessary study personnel. For analysis, this data is de-identified with participants assigned a study identification number ______. The data will be kept for 5 years.

6.2 Data Analysis

Data from the run-in participants will be analyzed separately from the data from the general study participants. Both cohorts will be analyzed using the ITT and Per Protocol definitions, and endpoints described previously.

Changes in measurements from baseline, to the end of each phase, to exit will be assessed. Participants will serve as their own controls and comparisons will be made to no change. One sample t-test will be used for numerical data. Fisher's Exact or Chi square will be used for categorical data.

All deviations from the study protocol will be identified, recorded and analyzed.

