Recruitment Potential subjects will be identified via advertisement at outdoor locations (i.e. flea markets, outside of movie theaters, shopping malls, train stations, stores that sell cigarettes), print media (i.e., local newspapers, billboards), web media (i.e., Craigslist, Facebook, Survey Monkey, Instagram, Twitter, Google Ads, Reddit, smokefree.gov) and through clinical research recruiters. Study Session Potential participants will complete an online screening form. Eligible participants will be called to confirm eligibility, discuss the study, and have their questions about the study answered. Interested eligible participants will then be emailed the registration link, which includes the electronic informed consent. After providing electronic informed consent, subjects register online and receive the COBSS device. Baseline questionnaires (demographics, smoking history, and attitude towards smoking) are completed, and subjects then self-train to use the COBSS (which includes the CO Breath Sensor and Breath Sensor App, or BSA) and the Pivot App. The BSA is required for the breath sensor to communicate with the subject's smartphone and allows basic viewing of CO sample values. The Pivot App comprises 5 sequential phases (Explore, Build, Mobilize, Quit and Secure). The Pivot App provides the user with information about CO sample values and CO trends, as well as the ability to log cigarette events (when subject smokes), view cigarette consumption trends, view instructional videos, complete educational activities and challenges, and engage with a coach. During the registration process, subjects are paired with a live coach who will provide support using in-app text messaging during the study. During the study, subjects log their cigarette events in the Pivot App and submit breath samples using the CO Breath Sensor. They also complete short (2-8 minutes) activities in the Pivot App, create a quit plan, and periodically engage with their coach. The primary phase of the study, during which participants are using the Pivot program, is 14.5 to 18.5 weeks in duration, depending on participant relapse/exit/re-entry rates and navigation of the phases of the Pivot App journey (Build is self-guided and lasts 1-28 days). Three months after completing the primary phase of the study, participants are asked to complete a final exit questionnaire. Questionnaires assessing smoking behavior, attitude towards smoking, quality of life, engagement with the program and feedback on the program are conducted at baseline, at the end of each Pivot App phase and at 3 months after completing the primary phase of the study. In addition, more detailed user

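### After Explore, the readiness, success and difficulty ratings come only from participants who progress, so the t-test of change to the end of Build or Mobilize can show a gain when the ITT cohort has not changed

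*Combined protocol and SAP*

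**What the plan says.** Section 6.2 (Data Analysis) states "Changes in measurements from baseline, to the end of each phase, to exit will be assessed". It continues "Participants will serve as their own controls and comparisons will be made to no change" and "One sample t-test will be used for numerical data". It applies the ITT and Per Protocol definitions, but gives no rule for a missing rating and no sensitivity analysis.

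The question table at the end of section 5.3 marks readiness to quit, expected success and difficulty staying quit (each 1-10) at Baseline, Explore, Build and Mobilize. The cells for Quit, every Secure time point and the 6-month follow-up are blank. The questionnaires follow the end of a phase, not a calendar date, and section 4.2 says "Phase completion is defined as completing the last in-app activity from that phase" (Secure has its own rule).

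The phase descriptions in section 5.3 tie progress to the attitudes being rated:

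- **End of Explore:** scores on readiness, confidence and perceived difficulty decide which Build module comes first.
- **Build:** "User must choose a quit date to unlock PTQ", Prep to Quit (PTQ) being one of four modules.
- **Mobilize:** "Quit date must be set within 14 days, but user can push out quit date during Mobilize", and all seven activities must be finished before moving on.

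Section 4.3.1 allows up to 20% of the general sample to be people not thinking of quitting.

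The documents disagree on later attitude data. The Protocol Summary says questionnaires, including those on attitude towards smoking, "are conducted at baseline, at the end of each Pivot App phase and at 3 months after completing the primary phase of the study". The Schedule of Study Activities places a questionnaire on thoughts about smoking in the Secure column. The question table has no such ratings after Mobilize.

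**The concern.** A participant who stops in Build has no later point in the question table at which the three ratings are asked. The change to the end of Mobilize is computed only in people who set a quit date and finished the activities.

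Pairing each person with their own baseline removes differences in baseline level. It does not remove selection on how ready a person was close to the later rating, which is plausibly what setting a quit date reflects. People whose readiness happened to rise are kept and those whose readiness fell are lost, so the mean change among those kept can be positive when the cohort mean has not moved. With no control arm, nothing in the design would reveal this.

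Attitude change matters to the plan: section 4.10 uses a mean change of 1 or more in these ratings as one of its grounds for the sample size.

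**Working it through.** **The plan's own figure.** Section 4.10 expects 100 or more of 260 at the last time point (100/260 = 38%) and says this detects a mean change of 1. SD, alpha, sidedness and power are not given, so the figure cannot be reproduced. At two-sided 5% and 80% power, n = 100 allows an SD of change up to √100 × 1/(1.96 + 0.84) = 3.57. The claim is plausible but not verifiable. It also refers to a time point at which the question table collects no such ratings.

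**Inputs for the bias.** From the documents: 260 participants, a 1-10 scale, and a one-sample t-test against zero. Assumed: mean 7, SD 2, no true change, correlation 0.5 between baseline and the later rating and between baseline and readiness at date-setting, and a share f reaching the end of Mobilize, namely those with the highest readiness at date-setting. Let r be the correlation of that readiness with the later rating.

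**Formula.** Expected change among those kept = SD × (r − 0.5) × φ(c)/f, where c is the normal quantile at 1 − f. For f = 0.5, φ(0)/0.5 = 0.798, so the change is 2 × 0.798 × (r − 0.5). The SD of change is about 2 × √(2 × 0.5) = 2, so with 130 people the standard error is 2/√130 = 0.175.

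| r | Formula gain | Approx. rejection | Simulated gain | Simulated rejection |
|---|---|---|---|---|
| 0.5 | 0 | 5% | 0 | about 5% |
| 0.6 | 0.16 | 15% | 0.15 | 15% |
| 0.7 | 0.32 | 44% | 0.31 | 49% |
| 0.8 | 0.48 | 78% | 0.47 | 83% |

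The simulation used 4,000 trials per setting, with ratings rounded and bounded to 1-10. Bounding and selection shrink the SD of change, so rejection runs slightly above the approximation. With f = 0.4 the gain runs from 0.18 to 0.56 and rejection from about 17% to 88%.

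**Other selection models** (mean 6, SD 2, equal correlations of 0.5, zero cohort change):

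- Full selection on readiness at the time of the later rating: +0.98, +0.65 and +0.35 when 40%, 60% and 80% complete.
- Weak selection (correlation 0.25 with that readiness): +0.23, +0.16 and +0.08.
- Random dropout, or selection on the Explore score alone: 0.
- Selection on baseline readiness alone, 60% completing: −0.65, a false loss.
- Rating all 260 regardless of progress: rejection stays near 5%.

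**Do simple analysis repairs work?** Setting the change to zero for people not rated does not: with full selection and 60% completing, the mean is 0.6 × 0.65 = +0.39, significant in 99% of runs. A missing-at-random regression on the Baseline and Explore ratings, which approximates a mixed model, does worse than the t-test. With the Explore rating correlating 0.6 with the others and f = 0.5, the estimated cohort gain is 0.23, 0.45, 0.66 and 0.87 for r = 0.5, 0.6, 0.7 and 0.8. The paired change subtracts all of the raised baseline of those kept; the regression corrects for only part of their raised later rating.

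**Does a fixed-day rating work?** Take r = 0.7 and f = 0.5. The 130 who progress average +0.31, and the other 130 must average −0.31. If all who progress reply, and 30% of the others (39) reply at random, the mean is 0.31 × (130 − 39)/169 = 0.17. If 70% (91) reply, it is 0.31 × (130 − 91)/221 = 0.05.

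**The case against.** Four stronger readings are tempting, and the documents do not support them.

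- **Nobody without a quit date is rated at the end of Build.** The quit-date requirement is explicit for Mobilize. For Build it is inferred from Prep to Quit being one of its modules; no sentence says Build cannot be finished without it.
- **Those who stop are never asked again.** That rests on the question table alone, and the Protocol Summary and the Schedule of Study Activities point the other way. The conflict is real, although a rating at exit would not supply the missing end-of-Build and end-of-Mobilize values.
- **The results are biased upward.** Direction and size depend on correlations and phase-reach rates that the documents do not give. Some barriers to progress concern engagement more than attitude, such as finishing activities; staff reminders and payment per questionnaire (section 4.5) may also influence who responds. The calculation models one rating, and success and difficulty need not follow date-setting in the same way.
- **The plan presents phase completers as the whole cohort.** Section 6.2 does not say so. Section 4.2 defines the Per Protocol set, under quit rates, as those who complete the relevant survey, and a within-person test validly describes those people.

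It is also fair that attitude is an additional endpoint, and that in the main scenarios the artefact stays below the 1-point change in section 4.10. What remains is that naming an ITT set cannot help when those who stop have no rating and no missing-data rule exists.

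**Conclusion.** The concern holds in conditional form. If progress depends on readiness near the time of the later rating, the planned t-test can show a gain to the end of Mobilize, and probably to the end of Build, in an unchanged ITT cohort. Under the assumed values with half reaching the end of Mobilize, the spurious gain is about 0.15 to 0.47 points and rejection about 15% to 83%, against a nominal 5%. At r = 0.5 there is no bias, and selection on baseline readiness would produce a false loss. No figure was worked out for Build separately.

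The primary endpoint, phase completion, is untouched. This is a worthwhile improvement to a secondary analysis, not a defect that must be cured before the study can answer its main question. It is best made before enrolment, because ratings never collected cannot be recovered afterwards.

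**What to change.** 1. Email the same three ratings to every ITT participant on one fixed day after onboarding, whatever phase they are in. Make change from baseline to that day the ITT attitude analysis. Report the number responding and add a missing-not-at-random sensitivity analysis, since people who have disengaged are the least likely to reply.
2. Present the end-of-Build and end-of-Mobilize changes as results among those who progressed, with the number rated at each phase, and not as an effect in the cohort.
3. Do not rely on a mixed model of the phase-end ratings alone; it can enlarge the bias.
4. Reconcile the Protocol Summary and the Schedule of Study Activities with the question table on whether attitude is asked at Secure and at 3 months after the primary phase.

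The cost is wording in sections 5.3 and 6.2 and one three-item online questionnaire, sent through the email contact already in use. The reported attitude gain may be smaller.
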